8.1 Binary secondary endpoints

Secondary outcomes **S1**, **S2** and **S4** are binary. For **S1** and **S2**, we will first compute the logarithm of the risk ratio and its confidence interval using a GEE approach [17], again to account for a potential within-patient correlation. Unlike for the primary analysis, here we will use a log-linear model. Specifically, the variance and link functions that define the GEE will be that of a binary family with a log link. Here again, we will use an independent working correlation structure, for the same reasons mentioned above. To compute the point estimate of the risk ratio and its confidence interval, we will then exponentiate the fitted log of the risk ratio and its confidence interval. We will not adjust for baseline variables in this analysis, mainly for three reasons already mentioned in Section 5.6. First, non-linear models do not directly provide marginal effect estimates [10]. Second, the baseline covariates are not expected to be substantially prognostic of the outcomes and third, because of the limited (effective) sample size. An example of R code corresponding to this analysis is provided in appendix A.2.

For outcome **S4** (mortality), we expect very few events (if any), say less than 1% (so, ≤ 2 in the dataset). Hence we will use an exact method instead of a GEE approach, as the asymptotic approximations implicitly used by a GEE approach would be very questionable. The method will not account for the within patient correlation, as we are not aware of any exact method that could do that. But, this is a relatively minor limitation when the risks are very small. Specifically, we will use an exact unconditional test using the score statistic ordering as in Nielsen et al. [19], and implemented in the `uncondExact2x2()` function of the R package `exact2x2`; see [8] for the mathematical details and Appendix A.3 for the specific R code that we will use.

8.2 Quantitative secondary endpoints

Secondary outcomes **S3** (days alive without fever within 28 days) and **S5** (time to bone marrow recovery) are quantitative outcomes. They will be analyzed by estimating the median within each arm and their difference, together with two-sided 95%-CIs. The standard errors to compute the CIs will be computed using non-parametric cluster bootstrap (using $B=1000$ replicates). This means that we will bootstrap the patients, not the episodes, following “Strategy 1” in Section 3.8 of Davison and Hinkley [4]. An example of R code corresponding to this analysis for secondary outcome **S3** is provided in appendix A.4.

Unlike for **S3**, for secondary outcome **S5** (time to bone marrow recovery) the estimator of the median that we will use will not be the standard one. That is, we will not use the `median()` function of R as described in Appendix A.4. This is because we expect to observe interval censored data, as already discussed in Section 5.4. Instead, we will proceed as follows. First, we will use an appropriate and well known method to estimate the cumulative incidence function from interval-censored data: the nonparametric maximum likelihood estimator method implemented in the `icfit()` function of the R package `interval` (see [9] or [7, Sec. 16.5] and references therein). Second, from the estimated cumulative incidence function, we will then estimate the median as $\inf \{t : \hat{F}(t) \geq 0.5\}$, where $\hat{F}(t)$ denotes the estimated cumulative incidence function at time t [2].

9 Analyses supporting exploratory outcomes

The main analyses of the exploratory outcomes detailed in Section 4.4 will also use the “All episodes analysis set” and corresponds to ITT analyses. They will be analyzed using the same methods as those used for the secondary outcomes, as outlined in Section 8.1. Specifically, **E1** (mortality within 3 months) will be analyzed as secondary outcomes **S4** (mortality within 28 days) while **E2** (new initiation of antibiotic treatment within 28 days) will be analyzed as secondary outcomes **S2** (new episode of neutropenic fever within 28 days).

10 Other analyses

10.1 Additional outcome analyses

10.1.1 Rates of SAE during neutropenia

We will compute the rate of SAE during neutropenia, within 28 days from treatment initiation, among children that are:

- (i) currently treated with antibiotics
- (ii) not currently treated with antibiotics.
- (iii) not currently treated with antibiotics, but have stopped antibiotic treatment less than three days ago.

For the primary analysis of these rates, we will pool the data of the two arms. The rationale for pooling the data is that antibiotic treatment are expected to have a short term effect. Hence, it seems reasonable to assume that a child currently treated with antibiotics is approximately similarly protected no matter how long ago the treatment has started, either many days ago (as typical in

the “long” arm) or just a few days ago (as typical in the “short” arm). We will compare the rates via rate ratios. The rate ratio of main interest is that comparing the rates of the first and third groups. Indeed, an interesting research question is: *“Is there an increased risk of SAE just after stopping the antibiotic treatment during neutropenia?”* (here “just after stopping” is defined as “within three days from stopping”). Comparing the rates of the first and second groups is also of interest.

To compute the rates, we will divide the number of events by the total time duration (days) at risk, as commonly done. Note that by definition of the rate of interests (during neutropenia), a time period (day) is not “at risk” if ANC is not $< 0.5 \times 10^9$ cells/L. Time at risk will be expressed in days, but computed as detailed in Section 5.7.2. This means that a continuous time scale will be used, not a discrete one. Exact Poisson inference will be used to compute 95% CI for the rates and the rate ratios using the `poisson.test()` function of R. Specifically, we will look at the rate of the first SAE. Although SAEs is a potentially recurrent event, we will investigate the rate of the first of possibly several SAEs. Descriptive statistics about children experiencing more than one SAE (if any) will be provided for completeness. We will consider presenting a descriptive plot similar to that of Figure 1 to transparently report the raw data about numbers of events and days at risk and show how these analyses summarize these raw data.

For completeness, we will also redo the analyses stratified per arm (i.e., without pooling the data).

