4.1 Primary objective, endpoint and estimand

The two treatment strategies (interventions) being investigated are the following.

- **Experimental (“short”):** discontinuation of antibiotics, despite neutrophil count $< 0.5 \times 10^9$ cells/L, after 48 hours of apyrexia and clinical stability. A child is considered clinically stable by the treating physician when there is resolution of all symptoms and signs of infection, and normalization of vital signs including heart rate, respiratory rate, oxygen saturation, blood pressure, and daily diuresis.
- **Control (“standard” or “long”):** discontinuation of antibiotics when either i) neutrophil count is $\geq 0.5 \times 10^9$ cells/L, and the child is afebrile and clinical stable or ii) the child has received 10 days of antibiotics and has been afebrile and clinically stable for 7 days.

The two treatment strategies are followed from randomization until neutrophil recovery (i.e. neutrophil count $\geq 0.5 \times 10^9$) or 28 days, whichever comes last. In case of relapsing fever, the patients continue to be treated according to the same treatment strategy (“short” or “long”). Randomization could occur from 36 hours after initiation of antibiotics until 48 hours of apyrexia and clinical stability (when the two treatment strategies can start to differ).

The primary outcome is the number of days without antibiotic treatment within the first 28 days after treatment initiation. For each of the 28 days, the information of whether the patient received antibiotics has been collected. The typical reasons for restarting antibiotics are new onset of fever, typically:

- febrile neutropenia (without documented infection)
- fever with or without neutropenia due to a possible or proven bacterial infection, including bacteremia (bacterial infection in the blood stream), pneumonia, skin infection, gastroenteritis or typhilitis (infection in the gut), urinary infection or other types of focal infections; side effects to chemotherapy that is accompanied by fever, such as pancreatitis

Restarting antibiotics might also happen without new onset of fever, for instance in case of suspicion of infection (e.g. focal symptoms from skin, lungs, gastrointestinal, etc).

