The primary clinical question of interest is: *“Is the mean number of days alive without antibiotic treatment, within 28 days after treatment started, larger when children receive the “short” treatment duration strategy than when they receive the “long”, among children with cancer who started antibiotic treatment for high risk neutropenic fever of unknown origin, regardless of any intervention”*

during the follow-up needed to ensure good clinical care?

Accordingly, the primary estimand is described by the following attributes:

- Population: children (aged 0-17) with cancer receiving antibiotic treatment for high risk neutropenic fever of unknown origin 48 hours after presentation. In particular, children with
 - a single temperature of at least 38.5° C , or a temperature above 38.0° C sustained over a 1-hour period (auricular, oral or rectal), at presentation.
 - an absolute neutrophil count $< 0.5 \times 10^9$ cells/L and an expected duration of neutropenia of more than 7 days at presentation.
 - a negative blood culture (or other clinically relevant culture) 48h after the start of the culture.
- Endpoint: number of days alive without antibiotic treatment within the first 28 days after treatment initiation.
- Treatment: The investigational interventions (“short” vs “long”, as defined above) regardless of adherence and of any subsequent treatment decision or intervention during the follow-up needed to ensure good clinical care (“treatment policy strategy”, see [14]).
- The intercurrent event “any subsequent treatment decision or intervention needed to ensure good clinical care” is addressed by the treatment condition of interest attribute (“treatment policy strategy”, see [14]). The intercurrent event adherence to the investigational intervention is also addressed by the treatment condition of interest attribute (“treatment policy strategy”, see [14]). There are no other relevant intercurrent events anticipated.
- Population-level summary: Difference in means between treatment conditions.

Remarks:

- (i) The “treatment policy strategy” for the intercurrent event “adherence to the investigational intervention” is consistent with an Intention-To-Treat principle/analysis discussed in Section 5.1. In our context, “adherence” is defined as “continue antibiotic treatment” as long as defined by the treatment strategy (not shorter, not longer).

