- (ii) It might happen that the blood culture (or other clinically relevant culture) turns positive late (after randomization), even though this is not expected to happen (or only in a few cases). If this happens, standard treatment that targets the newly identified cause of infection will be given identically in both arm. This is implicitly meant by the statement “regardless of any subsequent treatment decision or intervention during the follow-up needed to ensure good clinical care” in the treatment and intercurrent event attributes above.

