4.2 Secondary endpoints

There are five secondary outcomes:

S1: Severe adverse event (SAE) within 28 days, defined as any of these events:

- Severe sepsis, defined as either (i) vasoactive treatment requirement or (ii) fluid bolus requirement $>20\text{mL/kg}$ or (iii) respiratory support requirement (mechanical ventilation).

- Fever with positive blood culture. For possible contaminants, at least two positive culture bottles were required. Possible contaminants include coagulase negative staphylococcus, micrococcus spp., non hemolytic streptococcus, Corynebacterium spp, Propionibacterium spp, Bacillus spp.
- Severe focal infection highly suspicious of bacterial cause, requiring antibiotic treatment (e.g. lungs, abdomen, CNS, skin)
- Death

S2: New episode of neutropenic fever within 28 days.

S3: Days alive without fever within 28 days.

S4: Mortality within 28 days.

S5: Time to bone marrow recovery (up to 3 month), defined as the time from start of treatment to first absolute neutrophil count (ANC) $\geq 0.5 \times 10^9$ cells/L.

Note: see Section 5.7 for details about the definitions of fever, neutropenia/neutropenic, **S2** and **S3**.

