5.7 Pivotal definitions

5.7.1 Time zero

To define many outcomes, e.g., **S2**: “new episode of neutropenic fever within 28 days”, we need to precisely define when the time starts. This is necessary to properly define the time window, e.g. “within 28 days”. In this SAP, we define that time (i.e., time zero) at the time of treatment initiation, not at time of randomization, which should occur appropriately 48 hours later. This is consistent with the definition of the primary outcome (see Section 4.1) and it should facilitate the interpretation of the results.

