5.7.4 Neutropenia and episode of neutropenic fever

To define **S2** (New episode of neutropenic fever within 28 days), we also need to define neutropenia. Start of neutropenia is defined as the time when neutrophil counts are first observed $< 0.5 \times 10^9$. Time of stop of neutropenia is defined as the first time neutrophil count is observed $\geq 0.5 \times 10^9$ after start time. An episode of neutropenic fever starts when the child is first observed with both neutropenia and fever. It stops when either fever or neutropenia stops (whichever comes first).

Durations of neutropenia expressed in days are computed as the time difference between two dates and times: that of neutropenia stop and that of neutropenia start. Hence, treatment durations expressed in days are not whole numbers, but decimal numbers. This definition of neutropenia is used to compute secondary outcome **S2** and some rates (See Sections 4.2).

6 Analysis Sets

- The “**All episodes analysis set**” consists of all randomized episodes.
- The “**Per protocol analysis set**” consists of all randomized episodes except those for which the child did not receive the “short” or “long” treatment strategy to which he or she was randomized. These children will be identified as detailed in Section 10.2.3.

7 Analyses supporting the primary objective

The main analysis supporting the primary objective and corresponding to the estimand detailed in Section 4.1 will use the “All episodes analysis set” and corresponds to an ITT analysis.

To estimate the between arm difference in means with a 95% confidence interval and a p-value, we will use a multiple linear model (aka ANCOVA). The model will be fitted via GEE [17] and the standard errors will be computed accordingly, to account for possible within-patient correlation, as already mentioned in Section 5.5. We will use an independent working correlation structure, as we expect the correlation to be negligible and because additional assumptions might be needed for other choices [24]. The variance and link functions that define the GEE will be that of a gaussian family with an identity link, as commonly used for quantitative outcomes. Baseline covariates included in the model will be:

²pricisely, that of fever stop or 28 days after treatment initiation, whichever comes first (because we compute the sum within 28 days).

- Age at randomization

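### The SAE rate analysis in SAP 10.1.1 starts its clock before randomization, so lead-in time conditioned on eligibility enters only the on-antibiotic comparator group

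*SAP*

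**What the plan says.** Section 10.1.1 introduces the analysis with "We will compute the rate of SAE during neutropenia, within 28 days from treatment initiation, among children that are" (i) on antibiotics, (ii) off antibiotics, or (iii) off antibiotics for less than three days. Only time with ANC below 0.5 × 10⁹/L is at risk, only the first SAE counts, the arms are pooled, and a per-arm repeat follows. On the contrasts it states: "The rate ratio of main interest is that comparing the rates of the first and third groups". The ratio of (ii) to (i) is also of interest. No delayed entry or landmark is mentioned.

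Four other places bear on this:

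- Section 5.7.1 sets time zero "at the time of treatment initiation, not at time of randomization", and puts randomization about 48 h later.
- Section 4.1: "Randomization could occur from 36 hours after initiation of antibiotics until 48 hours of apyrexia and clinical stability". It adds that this end point is where the two strategies can begin to diverge. The population must have "a negative blood culture (or other clinically relevant culture) 48h after the start of the culture".
- Section 6: the main analysis set "consists of all randomized episodes". Section 10.1.1 names no set, but the only other one defined is a subset of this.
- Section 4.2 lists four SAE components: severe sepsis, "Fever with positive blood culture", severe focal infection, and death.

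**The concern.** An episode must reach randomization to be analysed at all. The time from antibiotic start to randomization is therefore observed only in children who survived it and, largely, whose culture was negative at 48 h. Death and bacteremia are SAE components, so eligibility partly determines which events can appear in that time. All of it is on antibiotics, so it falls in group (i) and none of it in groups (ii) or (iii).

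For S1 and the primary outcome the same time zero does little harm, because arms are compared and randomization balances the lead-in. Section 10.1.1 compares antibiotic status, and there the lead-in sits on one side only. The per-arm repeat keeps the same structure.

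At stake is the comparator for the question the section asks: whether SAE risk rises just after antibiotics are stopped during neutropenia. There is a second effect. Because only first SAEs count, an SAE before randomization also removes that episode's later time, including its off-antibiotic time.

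**Working it through.** **Source of the on-antibiotic time.** The SAP gives no figure for the rate analysis. Its sample-size calculation (11.1) is the only source of expected antibiotic days, and it reproduces: 2 × 6.5² × (1.96 + 1.282)² / 3² = 98.7, so 99 per arm, 198 in total, and 198 / 0.9 = 220.

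**Inputs**

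- T, on-antibiotic days per episode: 28 − 16 = 12 (short) and 28 − 13 = 15 (long), mean 13.5. Not all of these days need be neutropenic, so on the planning values 13.5 is an upper figure for group (i).
- L, lead-in days: 1.5 (36 h) to 2 (48 h). This assumes ANC below 0.5 from presentation, as in 4.1. Section 7 keeps a covariate category of 0.5 or above at presentation, so L may be shorter for some episodes. It is longer where randomization came later.
- f, the SAE rate in the lead-in divided by the later on-antibiotic SAE rate: not given, so a range is shown.

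**Formula.** The planned group (i) rate, relative to the rate after randomization, is (T − L + L·f) / T. Both ratios, (iii)/(i) and (ii)/(i), are therefore multiplied by T / (T − L + L·f). This ignores the later time lost after an early SAE.

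**Share of group (i) time.** 1.5 / 13.5 = 11.1%; 2 / 13.5 = 14.8%. By arm with L = 2: 2 / 12 = 16.7% (short) and 2 / 15 = 13.3% (long).

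**Multiplier**

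| T | L | f = 0 | f = 0.5 | f = 1 | f = 2 |
|---|---|---|---|---|---|
| 13.5 | 1.5 | 1.13 | 1.06 | 1.00 | 0.90 |
| 13.5 | 2 | 1.17 | 1.08 | 1.00 | 0.87 |
| 10 (assumed) | 1.5 | 1.18 | 1.08 | 1.00 | 0.87 |
| 10 (assumed) | 2 | 1.25 | 1.11 | 1.00 | 0.83 |

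For example, 13.5 / (13.5 − 2) = 1.17 and 13.5 / (13.5 − 2 + 4) = 0.87.

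**Against sampling error.** Take 100 episodes (11.2), so 100 × 13.5 = 1350 group (i) days, and 100 × 3 = 300 group (iii) days, the most that one stop per episode can give. Assume 10 and 5 first SAEs. The exact Poisson ratio is 2.25 (95% CI 0.60–7.22). If the lead-in held no event (f = 0, L = 2), starting at randomization leaves 1350 − 200 = 1150 days and gives 1.92 (0.51–6.15). The shift is small beside either interval.

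**The case against.** The best case for leaving the text alone has four parts.

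- **Standing.** This is an additional analysis, added late (Section 12, item 5). Section 5.3 confines formal testing to the primary estimand. The sign of the bias is unknown, and at f = 1 there is none. This stands and limits the weight of the point.
- **Strength of the conditioning.** A reader might infer that the lead-in is fully immortal time, so that the plan overstates the danger of stopping. The documents do not support that. Section 8.1 expects mortality below 1%, so excluding early deaths removes almost nothing. The culture rule screens only cultures positive by 48 h. Early severe sepsis is not stated to bar randomization; if it occurred, it would count in group (i) and lower the ratios. f = 0 is an extreme bound.
- **Mitigation already planned.** Cumulative incidence curves for S1 (10.1.3) will show early SAEs, but by arm and not by antibiotic status. The per-patient plot with SAEs marked (10.1.1, 10.2.7) would show them by status, but it is only under consideration. Neither changes the ratio. Nor does the pooling rationale: similar protection whenever treatment began does not address time filtered by eligibility.
- **Side effects of the remedy.** Randomization may come as late as 48 h of apyrexia and stability, which is also where the short strategy stops. Short-arm episodes randomized then keep almost no first-course on-antibiotic time. In the per-arm repeat, the short-arm group (i) could consist mainly of restarted courses, which 4.1 says typically follow new fever. This stands and shapes the fix.

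**Conclusion.** The point holds as a minor-to-moderate one. Group (i) contains lead-in time that the other groups cannot contain, and its event count there is partly set by eligibility. At the planning values this is about 11–15% of group (i) time. It multiplies both ratios by 1.13–1.17 at the extreme f = 0, by 1.00 at f = 1 and by 0.90–0.87 at f = 2. The range widens if neutropenic on-antibiotic time is shorter than 13.5 days. The size rests on the sample-size assumptions, on neutropenia from presentation and on an unknown f, so no direction can be claimed. Sampling error is probably larger.

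Two further readings go too far. One is that time zero in 5.7.1 is wrong in general: it is balanced between arms for the primary outcome and S1, and those results are unaffected. The other is that the lack of a dating rule for cultures turning positive late is a fault of the SAP. Such detail may sit in the protocol, and 10.2.9 already reports those cultures with their timing.

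**What to change.** In the pooled analysis of 10.1.1:

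- Start risk time and event counting at randomization (delayed entry) for all three groups, and keep the end at day 28.
- Define the event as the first SAE after randomization.
- List SAEs before randomization by arm, and keep those episodes at risk afterwards.
- Show the from-initiation version as a sensitivity analysis.
- State that the ratio remains a non-randomized comparison, because a child enters group (iii) only after being judged afebrile and stable. The new clock start does not remove that selection.

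In the per-arm repeat, report both clock starts and interpret the short-arm ratio with caution, for the reason given under the objection. Leave time zero for S1 and the primary outcome as it is.

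**Cost.** This is SAP wording only, assuming randomization times are recorded. At least 1.5–2 days per episode, and any SAE in them, leave group (i). For the pooled analysis with 10 and 5 events, the approximate 95% factor is exp(1.96 × √(1/10 + 1/5)) = 2.93. It becomes 2.99–3.02 at f = 1 (8.89 or 8.52 expected group (i) events remain) and 3.06–3.11 at f = 2 (8.00 or 7.42 remain). The loss would be larger where randomization came later, and in the short arm alone.

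A small residue stays. Where randomization came at 36 h, up to 12 h before the 48-h culture reading remains in group (i): 0.5 / 12 = 4% of its time, a factor of at most 12 / 11.5 = 1.04.
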